**Table 1 key for time points when variables are measured.**

1=Pre-Testing; 2=Prior to daily treadmill intervention; 3=Baseline on treadmill;  
4=Tethered TPAD Treatment; 5=Post Treatment on treadmill; 6=Post Overground  
Training; 7= Post Testing; 8=1-Week Follow Up Testing

Domain to be Measured	Outcome Measure	Variable Name	Time Required	When
Measures of Participation and Overall Health				
1. Adherence	Attended Visits	ADHER	1 minute	1,2,7,8
Measures of Activity				
2. Perceived Tolerance	Perceived Exertion	RPE	1 minute	2,3,4,5,6
3. Physiological Tolerance	Heart Rate	HR	1 minute	2,3,4,5,6
Measures of Body Functions				
4. Load Symmetry	Load Force	Fz	1 minute	3,5
Overground Spatiotemporal Measures of Gait				
5. Stance Symmetry	Symmetry Ratio - Stance Time	STANCE	15 minutes	Measured Simultaneously 1,2,6,7,8
6. Swing Symmetry	Symmetry Ratio – Swing Time	SWING		
7. Time in Double Support	Double Limb Support Time	DS		
8. Stride Length Symmetry	Symmetry Ratio – Stride Length	StrLENSYM		
9. Stride Length	Mean right/left -Stride Length	StrLENGTH		
10. Stride Velocity	Mean right/left -Stride Velocity	StrVEL		
11. Gait Velocity	Time of 10MWT	10WTIME		
12. Balance	Berg Balance Scale	BBS	20 minutes	1,7,8

### **3. Data collection and handling**

Pre-Testing, Post-Testing and Follow Up gait assessments (percentage of time in stance, swing, double support, stride length, and stride velocity) will be recorded using APDM® inertial sensors as participants complete a series of three, 10 meter walk tests (10MWT). Gait velocity and Berg Balance Scale (BBS) results will be recorded on paper forms at the time of assessment. Baseline, Training and Post-Training measures of load force will be recorded via force plates embedded in the treadmill. Safety issues/injuries/falls and adherence will be noted on paper forms at day of visit. Measures of perceived exertion will be verbally taken and recorded on paper forms. Heart rate will be taken using a Polar H10 heart rate monitor and recorded on paper forms.

All assessment and intervention data will be coded by a participant identification code and entered into a Microsoft Excel Spreadsheet. This spreadsheet will be stored on a CUMC password secured and encrypted end point device. Hard copies of paper forms will be filed by participant identification code number, and kept in a locked file cabinet in the locked office of a member of the research team at CUMC. Only members of the research team will have access to the electronic and hard copy data. The code key for each participant will be stored in the hard copy of each file. No electronic code key will be made.

### **4. Definitions/Calculations**

The following section describes each measure used in the study. Calculated values will be noted in *RED*.

## **4.1 Feasibility Measures**

### **4.1.1 Safety**

#### **Assessed at each study visit**

All falls, injuries, and any safety concerns that arise will be recorded on paper forms and reported summarily.

### **4.1.2 Adherence**

Variable = ADHER

#### **Assessed at each study visit**

Attendance will be recorded on paper forms at each study visit.

### **4.1.3 Tolerance**

#### ***4.1.3.1. Ratings of Perceived Exertion***

Variable = RPE

#### **Assessed at each training visit at time points 2,3,4,5, and 6.**

Perceived exertion will be measured by the Borg Scale. The Borg Scale is displayed for participants throughout each training session. Individuals are read a script explaining the use of the scale (See script in Standard Operating Procedures Manual) and asked for a numeric value that represents their overall level of exertion. Responses will be recorded on paper forms.

#### ***4.1.3.2 Heart Rate***

Variable = HRmax

#### **Assessed at each training visit at time points 2,3,4,5, and 6.**

Measures of heart rate will be taken via Polar H10 monitor and recorded on paper forms. The maximum heart rate reached by each participant will be reported as a percentage of the participant's heart rate maximum.

$$\text{HRmax} = 220 - \text{participant's age}$$

$$\text{Individual Percentage of HRmax} = (\text{Measured HR}/(220 - \text{age})) * 100$$

## 4.2 Efficacy Measures

### 4.2.1 Force Measures

Variable = **Fz**

**Assessed at each training visit at time points 3 and 5.**

Measures of load force will be taken while the participant is ambulating on the treadmill during both Baseline gait (at minute 0-1 (BL1), minute 2-3 (BL2) and minute 4-5 (BL3)) and Post Training (during minute 0-1 (PT1), minute 3-4 (PT2), minute 6-7 (PT3) and minute 9-10 (PT4)). This will be recorded via force plates embedded under the treadmill belts. The magnitude of force in the downward, vertical direction (z) and time the force was exerted on each force plate (for each the paretic and non paretic limb) will be extracted and used for analysis. These forces and times will be multiplied to yield an impulse force, and symmetry ratios will be calculated from the impulse of the load force.

$$\text{Impulse Force} = \text{Fmagnitude} * \text{Ftime}$$

$$\text{Force Symmetry} = \text{FzParetic}/\text{FzNon-paretic}$$

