An engineer trained in the use of the TPAD will be present and record data while the physical therapist is supervising the participant during the treadmill portion of the intervention.

Data collected from baseline (Intervention Day 1) and post training (Intervention Day 5) will be used as a primary outcome of vertical Ground Reaction Force (GRF)**. Daily measures (Baseline to Post Training within day) will be used as secondary measures of GRF over the course of training.

Procedures are as follows:

- Reflective markers, safety harness, pelvic belt and arm sling will be placed as described in 'Intervention' section above.
 - The participant will be assisted onto the dual belt treadmill and confirmed gait speed established as described in 'Intervention' section above.
 - Force plates embedded under the dual belts of the treadmill will be activated for data recording of Forces in the vertical direction (F_z) as a measure of GRF. These recordings will occur during minute 1, 3 and 5 during 'Baseline' gait procedures as described in the 'Intervention' section above.
 - RPE** and HR** will be recorded before (at resting) and after 'Baseline' gait, at 10-minute intervals during TPAD force intervention, on completion of 'Post Training' gait, and lastly on completion of overground gait. These measures will be recorded on CRF_TPAD_Form_02.
 - Force plates will also be activated for data collection of F_z as a measure of GRF during minutes 1, 3, 5, 7, 9 of 'Post Training' gait procedures as outlined in the 'Intervention' section above.
 - These procedures will be repeated during daily intervention sessions.
- This will complete the Treadmill Assessment portion.**

D. Intervention

All interventional procedures are to be performed during week two of study participation. These sessions will occur daily for five consecutive days. The duration of each interventional session will be approximately one and one half hours (90 minutes).

[figure not shown]
Participants will be asked to wear gym shorts and comfortable walking shoes for each training session. If participants wear other clothing to the session (e.g. in winter months), they will be given the opportunity to change clothes prior to initiating any study procedures.

A licensed physical therapist will supervise all training sessions. Engineers experienced in operating the TPAD will be primarily responsible for the operating and running of the TPAD and treadmill during the training session.

1. Set up

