- c. During this time the participant will gain familiarity with treadmill walking (Baseline), and vertical force measures (Fz) will be recorded. This is explained in detail in the 'Assessments' section.
- d. Video recordings will be taken from a posterior view during minutes 3-4 of baseline gait.
- e. On completion of the five minutes of baseline gait, the supervising therapist will verbally tell the patient to hold on to the side hand rails, and the treadmill will be stopped.
- f. HR and RPE will be recorded on CRF_TPAD_Form_02 (See attached).
- g. Tethers will be attached to the pelvic belt.
- h. Participants will be offered a seated rest break. Time of rest break will be recorded.
- i. Reflective markers will be placed on the tethers at the point of attachment to the pelvic belt and at the level of the pulley/frame.

- j. A force of resting magnitude will be applied during static standing (enough force to keep tethers taut during gait, but this resting magnitude will be evenly distributed among the four force tethers along a horizontal plane at left/right anterior/posterior positions).
- k. A still image will be taken to ensure tethers are appropriately in place, and markers attached to tether attachment points will be removed.
- l. Once forces tethers are taut, the visual feedback monitor will be turned on and the supervising therapist will explain the role of feedback during the training.
 - Verbiage to be used:
 - “Do you see the 2 bars in front of you? The right/left (side of the paretic limb) represents your weaker leg. This bar moves depending on how much weight you put into your leg. Go ahead and lift your leg so you can see the bar move.”*** [Participant lifts leg and bar representing paretic limb lessens].
 - “Do you see the other bar? It is your target. On each step, I want you to try and get your right/left (paretic) bar up to the top of that target and keep it there as long as possible while you are walking. Do you have any questions?”*** [Participant is given an opportunity to ask questions for which a member of the research team will respond appropriately.]
 - “There will be points during training where this screen isn’t on. I still want you to think about the screen and put as much weight on your weaker leg and keep it there as long as possible – even when you do not see the screen. Do you understand?”***

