During this time vertical forces (F_z) will be taken for each the paretic and non paretic limb.

- t.** Video recordings will be made from a posterior view during minutes 5 of post training.
- u.** On completion of post training, participants will be assisted off of the treadmill and reflective markers, safety harness, pelvic belt and arm sling will be removed.
- v.** HR and RPE will be taken and recorded on CRF_TPAD_Form_02 (See attached).

3. Overground Training

- a. Participants will then initiate overground training for which they will ambulate in a quiet corridor and will receive verbal and gentle tactile cues to reinforce TPAD training. Overground training will be between 5-10 minutes. Duration of overground training period will be recorded.
 - Verbal cues will include:
 - “Remember to walk and put as much weight on your right/left (paretic) limb as possible and keep it there as long as possible.”
 - “Can you put more weight on your right/left (paretic) side?”
 - “A little more”
 - “More weight over here”
 - “Keep it/your weight there a little longer with each step.”
 - Tactile cues will include:
 - Gentle tapping at right/left (paretic) side.
 - Gentle tapping at right/left (paretic) quadriceps.
 - Light hand hold around pelvis with gentle weight shift onto paretic side.
- b. On completion of overground training, HR and RPE will be taken and recorded one additional time on CRF_TPAD_Form_02 (See attached).
- c. CRF_TPAD_Form_02 will be completed daily for each intervention session.
- d. Any incidents with patient safety during interventional procedures will be reported on CRF_TPAD_Form_02.
- e. Any missing visits** occurring during intervention will also be noted on CRF_TPAD_Form_02.
- f. This will conclude the training portion of the session.

VII. Participant Withdrawal

Participation in this study is voluntary. Participants will be allowed to withdraw from the study at any point. Withdrawal of participation from this study will not preclude individuals from participating in any future studies relating to stroke or for which the individual would be a potential candidate.

The participant may be withdrawn by a member of the research team if:

- The participant does not complete all Pre-Test Assessments.
- The participant completes < 4/5 training visits
- The participant does not complete Post-Test Assessment
- The participant sustains an injury while participating that would prevent s/he from completing study procedures

VIII. Risk / Benefit

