- Fractures
- Orthopedic related injuries
- Dizziness
- Severe fatigue that requires a ceasing of study procedures

In the case of an adverse event (AE), the participant will be evaluated immediately by the physical therapist present for all study procedures. If the AE persists, study procedures will be stopped, and the study MD notified to evaluate the participant. In such cases where applicable (e.g. fracture, ankle injury) the participant will be referred and assisted to the Emergency Room for immediate attention.

All AEs will be recorded and reported to the PI and IRB within 24 hours.

XI. Statistical Analysis

Please see attached Statistical Analysis Plan.

XII. Dissemination of Results and Publications

Results of this work will be analyzed and a manuscript prepared for publication. Full details of this work including prior work using the TPAD, background, study procedures, statistical analysis procedures and detailed results will be written and stored on file as a part of the final dissertation report.

[name], PT, DPT will serve as primary author on the dissertation with [name], EdD providing sponsorship. [name] will also serve as a primary author for manuscripts prepared discussing the feasibility and preliminary efficacy of the TPAD to reduce asymmetry in a population of individuals after stroke. [name], MS will serve as primary author for any manuscripts detailing technical specifics of implementing TPAD treatment in a population of individuals after stroke. Other participating members of the research team will be recognized in authorship in all manuscripts submitted for publication.

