Following these three visits of Pre-Test assessments, participants will return to complete five consecutive days of the training intervention. The intervention will consist of five consecutive days of TPAD training plus visual feedback training with a short over ground training (5-10 minutes) each day immediately following completion of treadmill based activities. After participants are readied for intervention, they will be assisted onto the treadmill and the treadmill will be initiated. Individuals will self-select gait speed with a physical therapist confirming speed is safe for the duration of training. Once gait speed is set, individuals will initiate five minutes of Baseline gait on the treadmill during which load force measures are recorded at minute 0-1 (BL1), minute 2-3 (BL2) and minute 4-5 (BL3). This Baseline gait will be followed by 40 minutes of tethered TPAD training with visual feedback provided. The amount visual feedback will be faded over the course of the five-day training. On completion of the tethered portion of training, participants will continue to ambulate on the treadmill for an additional 10 minutes during a Post-Training period. Measures of load force will be recorded during minute 0-1 (PT1), minute 3-4 (PT2), minute 6-7 (PT3) and minute 9-10 (PT4) of Post Training. Participants will then be assisted off the treadmill and an additional 5-10 minutes of over ground training will be conducted reinforcing weight shifting onto the paretic limb. Participants will be required to complete at least four days of training for data to be considered in the final analysis. Training sessions will last approximately 60 minutes (one hour) in duration.

On the fifth day of training, immediately following the final training session, participants will be allowed a 10-15 min seated rest break and over ground measures will be reassessed (Post

Test). All participants will be asked to return one week after completion of the intervention to undergo one final over ground assessment (Follow Up).

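### The protocol and the SAP schedule Post Training force recording in different minutes; followed literally, the protocol leaves two of the SAP's four windows unrecorded

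*SAP*

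**What the plan says.** **Post Training, protocol.** VI.C.ii (Treadmill Assessments) activates the force plates for vertical force "as a measure of GRF during minutes 1, 3, 5, 7, 9 of" the Post Training walk, which is five recordings. VI.D (Treadmill Training, step s) makes that walk 10 minutes long and says that vertical force "will be taken for each the paretic and non paretic limb" in that period, without naming minutes.

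**Post Training, SAP.** The text under Figure 1 (Trial Schema) instructs recording in "minute 0-1 (PT1), minute 3-4 (PT2), minute 6-7 (PT3) and minute 9-10 (PT4) of Post Training". SAP 4.2.1 repeats the same four windows, with force taken "during minute 0-1 (PT1), minute 3-4 (PT2), minute 6-7 (PT3) and minute 9-10 (PT4").

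**Baseline.** The protocol says "These recordings will occur during minute 1, 3 and 5 during" the Baseline walk. The SAP windows are 0-1 (BL1), 2-3 (BL2) and 4-5 (BL3).

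**Use of the data.** Protocol VI.C.ii states: "Daily measures (Baseline to Post Training within day) will be used as secondary measures of GRF over the course of training". SAP Study Outcomes 2.3 also makes within-day load symmetry secondary. SAP Statistical Analyses 3.1 compares the Baseline mean with each of PT1 to PT4 on the same day. SAP 2.2.1 is the primary load comparison, from the Baseline mean on Day 1 to Post Training on Day 5; it does not list the Post Training windows that enter the Day 5 value. On analysis the protocol says only "Please see attached Statistical Analysis Plan".

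**The concern.** The two documents give different instructions for the same measurement, and nothing maps the protocol's five recordings to the SAP's four windows. This is a contradiction and not an omitted detail. The SAP is consistent with itself about PT1-PT4, so the open question is whether the minutes it needs will be recorded. Staff working from the protocol's list would collect some minutes for which the SAP has no use and miss others that it tests by name. Minutes that were never recorded cannot be recovered. A set of windows chosen after the force data have been seen would no longer be prespecified.

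**Working it through.** The documents state no count of their own for this point, so there is no planned figure to reproduce. The check is an overlap of intervals.

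**Inputs**
- Protocol VI.C.ii: Baseline minutes 1, 3, 5; Post Training minutes 1, 3, 5, 7, 9.
- SAP 4.2.1: Baseline 0-1, 2-3, 4-5; Post Training 0-1, 3-4, 6-7, 9-10.
- Protocol VI.D: five training days; Baseline walk of five minutes (step e begins "On completion of the five minutes of baseline gait"); Post Training walk of 10 minutes.
- SAP 3.1: one comparison per Post Training window per day.

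**Step 1: what minute n means, judged from Baseline**
- Reading A, n-1 to n: minutes 1, 3, 5 become 0-1, 2-3, 4-5, which match 3 of 3 SAP Baseline windows.
- Reading B, n to n+1: they become 1-2, 3-4, 5-6, which match 0 of 3, and 5-6 falls outside the five-minute walk.

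The documents therefore support reading A.

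**Step 2: apply each reading to Post Training**

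| Reading | Protocol windows | SAP windows covered | SAP windows with no overlap |
|---|---|---|---|
| A | 0-1, 2-3, 4-5, 6-7, 8-9 | PT1, PT3 | PT2, PT4 |
| B | 1-2, 3-4, 5-6, 7-8, 9-10 | PT2, PT4 | PT1, PT3 |

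A centred reading (n ± 0.5) would half-cover all four Post Training windows and leave none empty. It would also only half-cover each Baseline window, and nothing in the documents points to it.

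**Step 3: comparisons affected**
- Planned: 4 windows × 5 days = 20.
- Without scheduled data: 2 windows × 5 days = 10, so 10/20 = 50%. The count is the same on readings A and B.

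**Step 4: the primary Day 5 value (illustration only)**

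Neither document gives by-minute force data. Assume that the symmetry ratio drifts linearly by D in total over the 10 minutes, with D between 0 and 0.10. The slope is then D/10 per minute. On reading A the mean window midpoints are:
- SAP, PT1-PT4: (0.5 + 3.5 + 6.5 + 9.5)/4 = 5.0 min.
- All five protocol minutes: (0.5 + 2.5 + 4.5 + 6.5 + 8.5)/5 = 4.5 min. The shift is 0.5 × D/10 = 0.05D, or 0 to 0.005.
- PT1 and PT3 only: (0.5 + 6.5)/2 = 3.5 min. The shift is 1.5 × D/10 = 0.15D, or 0 to 0.015.

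**The case against.** The strongest reply is that the loss is conditional. The SAP itself instructs recording at PT1-PT4, so a team that follows it would have all four windows. Protocol VI.D step s and SAP section 3 (Data collection and handling) describe Post Training force measurement without limiting the minutes. That stands: the documents disagree, but they do not show that data will be missing. On the other side, the protocol speaks of activating the plates in named minutes, SAP Table 1 gives the force measure as taking one minute, and no section states continuous capture.

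A second reply is that little information would be lost. On reading A the protocol minutes 2-3 and 8-9 directly abut PT2 and PT4. Under the drift assumption above, a one-minute displacement is 0.1D, at most 0.01. The protocol also takes five recordings against the SAP's four, so within-day change remains measurable early, midway and late. This stands too, and it limits the harm to comparisons that cannot be made as the SAP defines them.

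A reader might go further and infer that the SAP's missing-data rule (section 5, more than 15% missing) would remove load force from interpretation, since 2 of 7 daily windows is 28.6%. The documents do not support that. Section 5 does not say whether a window that was never scheduled counts as missing, or whether a variable means each window or the whole measure.

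**Conclusion.** The contradiction is real and worth fixing. On the convention that the Baseline schedules imply, PT2 and PT4 are not on the protocol's schedule. If the protocol list is followed literally and capture is not continuous, 10 of 20 within-day comparisons could not be made as defined.

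The harm falls on a secondary outcome of a 12-person, single-arm pilot. It would be tempting to conclude that the primary load result is compromised, but the documents do not support this: the Day 5 value stays computable, only from different minutes. The illustrative shift is at most 0.005 with all five protocol minutes averaged, or 0.015 with only the two shared windows. Both figures rest on the assumed linear drift and its assumed range. The SAP's rationale reports that gains in the preceding TPAD studies were retained after the tethers were removed, which suggests that drift may be small. The unlisted windows in SAP 2.2.1 call for a clarification and are not an error, since a mean over PT1-PT4 is the natural reading.

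**What to change.** 1. Before any Post Training force data from any training day are examined, bring both documents to one set of windows. Waiting until just before the Day 5 data are examined would be too late, because the within-day comparisons use all five days. Either change Protocol VI.C.ii to record PT1-PT4, or state there that force is captured continuously through the 10-minute walk.
2. If data already exist only on the protocol minutes, redefine the windows in the SAP's Trial Schema text, 4.2.1 and 3.1 to the recorded minutes. Using all five gives 5 × 5 = 25 within-day tests where 20 were planned. SAP 3.1 names no multiplicity correction, so the larger number should be stated.
3. As a clarification, say in SAP 2.2.1 that the Day 5 value is the mean of those same windows.

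**Cost.** Wording only, if nothing has yet been recorded; the documents do not show whether any force data exist. Minutes unique to the dropped schedule go unanalysed. On reading A these are 2-3, 4-5 and 8-9 if the SAP windows are kept (four recordings per session, not five), or 3-4 and 9-10 if the protocol minutes are kept.
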